## **Control exclusion criteria**

Controls will be excluded if they:

- refuse to participate in the study;
- are not eligible for influenza vaccination due to a condition listed in the summary of product
- characteristics;
- are institutionalised;
   are unable to give informed as
- are unable to give informed consent or follow an interview in their native language because of aphasia, reduced consciousness, or other reasons.

Pandemic vaccine: Controls will be excluded if they have previously been diagnosed with lab-confirmed A(H1N1)v after the start of the pandemic.

Reasons for exclusion will be documented.

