#### Influenza case

An influenza case will be defined as an ILI case with a respiratory sample positive for influenza.

A pandemic influenza case will be defined as an ILI case with a respiratory sample positive for A(H1N1)v.

**b** Indicators to define cases will be specified in the study annexes.

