#### Case inclusion criteria

Cases are eligible if they meet the above case definition and accept to participate.

**b** Oral informed consent or written informed consent according to country procedures, as specified in the study annexes.

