#### **Case exclusion criteria**

Cases are excluded if they:

- refuse to participate in the study;
- are not eligible for influenza vaccination due to a condition listed in the summary of product characteristics;
- are institutionalised;
- are unable to give informed consent or follow an interview in their native language because of aphasia, reduced consciousness, or other reasons.

Reasons for exclusion will be documented.

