# **3.7 Controls**

Various control groups can be selected depending on the available resources. All studies will include at least control group 1 (ILI influenza negative) as defined below.

- Seasonal vaccine: countries will assess whether other control groups could be used in addition to control group 1 (control group selection depends on feasibility).
- **b** The various control groups selected by each study will be detailed in the study annexes.
- Control group 1, ILI flu negative:
  - ILI cases that tested negative for influenza will be included in control group 1.
- Control group 2, non-ILI GP clients (density case-control design):
  - Controls will be selected among GP clients seen at the GP office and selected concurrently to cases (+/- one week from the date of consultation of the corresponding case). Controls will be selected by simple or systematic random sampling among clients who did not yet develop ILI during the influenza season.

**b** Procedures for selection in each of the studies will be detailed in the study annexes. If feasible, controls should be matched by age group (< 75 years; >= 75 years).

- Control group 3, GP clients (case-cohort design):
  - Controls will be selected randomly from a list of GP patients.
  - **b** Procedures for selection in each of the studies will be detailed in the study annexes.
- Control group 4, community controls (density case-control design):
  - Controls are randomly selected individuals living in the same geographical area (defined by postcode or other geographical/administrative division) as the corresponding case. Control individuals have not suffered from ILI during the current influenza season until the corresponding case became ill.
    - **P** Procedures for selection will be detailed in the study annexes.
    - If feasible, controls should be matched by age group (< 75 years; >= 75 years).
- Control group 5, community controls (case cohort):
  - Controls will be randomly selected individuals living in the same geographical area of the corresponding case.
    - **P** Procedures for selection will be detailed in the study annexes.
    - If feasible, controls may be matched by age group (< 75 years; >= 75 years).
- Control group 6, community controls (screening method):
  - For each of the target age groups, vaccine coverage of cases will be compared with the vaccine coverage of the population in the GP catchment area.

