vacc_07	Numeric (categorical)	0 = No 1 = Yes 8 = Do not know	Previous seasonal influenza vaccination 2007-08
anemia_spleen	Numeric (categorical)	0 = No 1 = Yes 8 = Do not know	Enlarged spleen, anaemia
cirrhosis	Numeric (categorical)	0 = No 1 = Yes 8 = Do not know	Cirrhosis
diabetes	Numeric (categorical)	0 = No	Diabetes and endocrine
		1 = Yes 8 = Do not know	
heart_dis	Numeric (categorical)	0 = No 1 = Yes 8 = Do not know	Heart disease
hema_cancer	Numeric (categorical)	0 = No 1 = Yes 8 = Do not know	Hematologic cancer
immuno	Numeric (categorical)	0 = No 1 = Yes 8 = Do not know	Immunodeficiency and organ transplant
lungdis	Numeric (categorical)	0 = No 1 = Yes 8 = Do not know	Lung disease
nonhem_cancer	Numeric (categorical)	0 = No 1 = Yes 8 = Do not know	Nonhematologic cancer
pregn	Numeric (categorical)	0 = No 1 = Yes 8 = Do not know	Pregnancy
ren_disease	Numeric (categorical)	0 = No 1 = Yes 8 = Do not know	Renal disease
dem_stroke	Numeric (categorical)	0 = No 1 = Yes 8 = Do not know	Dementia, stroke
rheumat	Numeric (categorical)	0 = No 1 = Yes 8 = Do not know	Rheumatologic diseases
severity	Numeric (count)	integer	Number of hospitalisations previous year for the chronic disease
gpvisit	Numeric (count)	integer	Number of GP consultations previous year
fs_bath	Numeric (categorical)	0 = No 1 = Yes 8 = Do not know	Requires assistance to bathe

Variable name	Туре	Values and coding	Definition
fs_walk	Numeric (categorical)	0 = No 1 = Yes 8 = Do not know	Requires assistance to walk
smoking		0 = Never 1 = Former 2 = Current 9 = Do not know	Never, former (stopped smoking at least 1 year before inclusion in the study), current smoker
antivir	Numeric (categorical)	0 = No 1 = Yes 8 = Do not know	Administration of antivirals
antivirdate	Date	dd/mm/yyyy	Date administration antiviral
antivirtype	Text		Type of antiviral (brand name)
prev_h1n1	Numeric (categorical)	0 = No 1 = Yes 8 = Do not know	Lab-confirmed A(H1N1)v prior to study.
res_home	Numeric (categorical)	0 = No 1 = Yes 8 = Do not know	Exclusion criteria: living in a residential home
contra	Numeric (categorical)	0 = No 1 = Yes 8 = Do not know	Exclusion criteria: contraindication for influenza vaccination
dens_cc	Numeric (categorical)	0 = No 1 = Yes	Exclusion criteria for density case- control: ILI symptoms in the season

This table represents a selection of confounders. Variables can be included or excluded as necessary.

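### Pandemic-vaccine analysis: previous laboratory-confirmed A(H1N1)v excludes controls but not cases, so in the test-negative comparison eligibility depends on the test result

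*Protocol*

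**What the plan says.** All references are to the Protocol.

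- **Controls (section 3.7, Control exclusion criteria).** For the pandemic vaccine only: "Controls will be excluded if they have previously been diagnosed with lab-confirmed A(H1N1)v after the start of the pandemic".
- **Case definition (section 3.5, Influenza case).** "A pandemic influenza case will be defined as an ILI case with a respiratory sample positive for A(H1N1)v". It is not limited to a first episode.
- **Case inclusion (section 3.6).** "Cases are eligible if they meet the above case definition and accept to participate".
- **Case exclusion (section 3.6).** The list opening "Cases are excluded if they" has four items: refusal, contraindication ("are not eligible for influenza vaccination due to a condition listed in the summary of product characteristics"), institutionalisation, and inability to consent or be interviewed. These match the general control exclusions. Prior A(H1N1)v is not among them.
- **Control group 1 (section 3.7), required in all studies.** "ILI cases that tested negative for influenza will be included in control group 1".
- **Data.** Prior confirmed A(H1N1)v is listed in section 3.12, in Annex 1 (prev_h1n1, defined as "Lab-confirmed A(H1N1)v prior to study") and in the Annex 2 minimum dataset, each time without a case/control restriction. Annex 1 marks some variables as exclusion variables, for example res_home: "Exclusion criteria: living in a residential home". The variables contra and dens_cc are marked in the same way; prev_h1n1 is not.

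**The concern.** In a test-negative design, cases and controls come from one pool of swabbed ILI patients and only the laboratory result separates them. Any other eligibility rule should be settled before the result is known and should apply to everyone in the pool. Here one rule applies to only one side of the result.

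If previously confirmed people differ from others in vaccine coverage, the cases contain a subgroup that the controls do not represent, and the odds ratio for pandemic vaccination shifts. The analysis affected measures pandemic VE in the target groups, which is a primary objective.

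**Working it through.** **Text comparison.** Take an ILI patient in the pandemic analysis with A(H1N1)v confirmed in an earlier episode.

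| New swab | Rule that applies | Outcome |
|---|---|---|
| Positive for A(H1N1)v | Case definition, inclusion and exclusion (3.5, 3.6) | Kept as a case |
| Negative for influenza | Control exclusion (3.7) | Removed |

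No other section supplies the missing case rule. The example models in Annex 6 do not contain prev_h1n1, though they are offered as guidance only and are written for seasonal vaccine.

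**Size.** The Protocol gives no figure for this point, so there is none to reproduce. What follows is an illustration.

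Inputs from section 3.13 (Pooled analysis, Pandemic vaccine): coverage 50%, OR 0.4 (VE 60%).

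Assumed inputs, not in the Protocol: share of the source population previously diagnosed (p), vaccine coverage among them (q), and their susceptibility relative to others (s). The vaccine OR is taken as 0.4 in both groups.

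Relative numbers of cases:
- vaccinated: (1 − p) × 0.5 × 0.4 + p × q × 0.4 × s
- unvaccinated: (1 − p) × 0.5 + p × (1 − q) × s

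Under the written rule, controls contain only people never diagnosed, so their vaccination odds are 0.5/0.5 = 1. The expected OR is then vaccinated cases divided by unvaccinated cases.

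*Strong protection, p = 10%, s = 0.1:*
- q = 10%: (0.18 + 0.0004)/(0.45 + 0.009) = 0.1804/0.459 = 0.393, VE 60.7%
- q = 70%: (0.18 + 0.0028)/(0.45 + 0.003) = 0.1828/0.453 = 0.404, VE 59.6%

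For p from 1% to 10%, q from 10% to 70% and s from 0 to 0.1, all results lie between 59.6% and 60.7%.

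*Weaker protection, p = 10%, s = 0.5:*
- q = 10%: (0.18 + 0.002)/(0.45 + 0.045) = 0.182/0.495 = 0.368, VE 63.2%
- q = 70%: (0.18 + 0.014)/(0.45 + 0.015) = 0.194/0.465 = 0.417, VE 58.3%

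*Extreme, p = 20%, s = 1 (no protection):* VE 71.0% at q = 10% and 53.0% at q = 70%.

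*Same exclusion for cases:* the terms in p × s disappear and OR = 0.2/0.5 = 0.4, so VE is 60.0% in every scenario.

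**Direction.** If previously diagnosed people have lower coverage than others, VE is overstated; if higher, it is understated. At q = 50% there is no shift.

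**Cases lost by the fix.** The previously diagnosed share of cases is at most 1.5% in the strong-protection range above. At p = 10% and s = 0.5 it is 4.4–6.9%. Out of 90 cases, that is about 1 (0.015 × 90 = 1.4) and about 4 to 6 (0.044 × 90 = 4.0; 0.069 × 90 = 6.2).

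**The case against.** **The effect needs an unusual chain of events.** A person already confirmed must develop a new sudden-onset ILI, be swabbed within seven days of onset and test positive for A(H1N1)v again. If prior infection protects strongly, few cases will be of this kind. This stands, and it is why the size is put as small.

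**Sampling error is much larger.** At the Protocol's minimum of 90 cases and 90 controls, with 50% coverage and OR 0.4, the expected counts are about 25.7 and 64.3 among cases and 45 and 45 among controls. The SE of log OR is √(1/25.7 + 1/64.3 + 1/45 + 1/45) ≈ 0.31, giving an approximate 95% interval for VE of 26% to 78%. This stands for single small analyses. Pooling reduces sampling error but does not remove this bias.

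**The control rule has a sound reason.** It restricts controls to people still at risk, which suits the density designs (control groups 2 and 4) as well. This also stands: the rule is not wrong in itself. But an at-risk restriction defines a source population without prior confirmed infection, and cases should come from that same population. The argument supports extending the rule.

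**The Protocol leaves room to repair it.** Study annexes may specify the indicators that define cases, the Protocol is to be updated, and the variable is collected. This makes the problem easy to correct. Leaving it to each site, however, could create differences between studies that the core protocol is meant to minimise.

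**Stronger readings that the document does not support.** A reader might infer that one infection would be counted as two cases and that a matching exclusion would prevent this. An exclusion based on an earlier episode does not touch repeat samples within one episode; those are a matter of record de-duplication. A reader might also infer a known direction of bias from a link between past infection and the decision to be vaccinated. No section documents such a link.

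**Conclusion.** The point holds for the pandemic-vaccine analysis with control group 1. The eligibility of a previously confirmed ILI patient depends on the new test result, and nothing elsewhere in the Protocol corrects this.

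The bias is probably small and of unknown sign. The working gives about 0.7 percentage points or less either way if prior infection protects strongly, and roughly 2 to 3 points at 10% previously diagnosed with half susceptibility. The share previously diagnosed, their coverage and their susceptibility are all assumptions; only the 50% coverage and the OR of 0.4 come from the Protocol. The extreme scenario (53.0–71.0%) marks an outer limit under no protection and should not be read as an expectation. No sample-size figure in the Protocol changes. This is a minor correction, worth making because it is nearly free.

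**What to change.** 1. In section 3.6, Case exclusion criteria, add for the pandemic-vaccine analysis the criterion that section 3.7 applies to controls. Any swabbed ILI patient with prev_h1n1 = yes from an earlier episode is then excluded whatever the new result. The current positive swab must not itself count as a prior diagnosis.
2. In Annex 1, label prev_h1n1 as an exclusion variable, as is done for res_home, contra and dens_cc.
3. Align the reference period. Section 3.7 and section 3.12 count from the start of the pandemic, Annex 1 says "Lab-confirmed A(H1N1)v prior to study", and the Annex 2 minimum dataset allows another date.

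Deleting the control exclusion instead would not be neutral when prior infection protects. With p = 10% and s = 0.1, the control odds become 0.46/0.54 = 0.852 at q = 10% and 0.52/0.48 = 1.083 at q = 70%. VE is then 1 − 0.393/0.852 = 53.9% and 1 − 0.4035/1.083 = 62.8%.

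Cost: one line of text and two small edits in the annexes, no new data collection, and the loss of a few cases.

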# 3.8 Exposure (vaccination)

## **Definition of vaccination status**

Seasonal vaccine: An individual is considered as vaccinated against influenza if the vaccination occurred more than 14 days before disease onset or more than 14 days before being selected as a control.

- Pandemic vaccine: An individual is considered:
  - *fully vaccinated* if he/she has received two doses of the vaccine more than 14 days before developing ILI symptoms or before being selected as a control;
  - *partially vaccinated* if he/she has received:
     a) only one dose of the vaccine more than 14 days before developing ILI symptoms (or more than 14 days before being selected as a control);
     b) a second dose less than 15 days before developing ILI symptoms (or more than 14 days before being selected as a control);
  - *unvaccinated* if he/she has not received any vaccine or if he/she has received one dose less than 15 days before developing symptoms.

The definition of the vaccination status may be revised and should be taken into account in the analysis if preliminary clinical data indicate that one dose is sufficient to confer protection, or that the immunisation delay is different from the currently assumed 14 days.

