# 2.2 Secondary objectives

- Pandemic and seasonal vaccine:
  - to estimate pandemic and seasonal VE:
  - in each of the participating countries;
  - by risk groups.
- Seasonal vaccine:
  - to estimate VE by influenza subtype;
  - to provide intra-seasonal VE estimates;
  - to monitor VE every year.
- Pandemic vaccine:
  - to provide early VE estimates;
  - to estimate VE for one and two doses;
  - to estimate VE by vaccine brand.

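### The pandemic partial-vaccination rule gives controls the window that defines full vaccination, so some controls fall in two categories and others, if classified by selection date, fall in none

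*Protocol*

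**What the plan says.** Section 3.8 (Definition of vaccination status) sets three categories for the pandemic vaccine.

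- **Full:** the person "has received two doses of the vaccine more than 14 days before developing ILI symptoms or before being selected as a control".
- **Partial (a):** "only one dose of the vaccine more than 14 days before developing ILI symptoms", with the same window given for selection as a control.
- **Partial (b):** "a second dose less than 15 days before developing ILI symptoms (or more than 14 days before being selected as a control".
- The **unvaccinated** line gives no reference date for controls. It applies "if he/she has not received any vaccine or if he/she has received one dose less than 15 days before developing symptoms".

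The section allows the definition to be revised if one dose proves sufficient or if "the immunisation delay is different from the currently assumed 14 days". Section 2.2 lists, for the pandemic vaccine, the objective "to estimate VE for one and two doses". Annex 5 defines only a binary pandemic exposure, panvacc, and a delay variable, panvaccdelay. Both are counted from symptom onset, and both are marked as needing modification if two doses are required.

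**The concern.** In whole days, less than 15 and more than 14 are complements. Partial (b) uses one for symptom onset and the other for selection as a control. The control half therefore describes people who have completed the course and passed the assumed delay, which is the full category. In a case-control study, exposure must be sorted by the same rule in both groups; otherwise the misclassification depends on case status and its direction cannot be assumed to be toward no effect.

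The estimates at stake are the one-dose and two-dose VE. This is a core protocol: each country analyses its own data first and the results are then pooled. Teams that resolve the overlap differently would add heterogeneity in the exposure definition itself.

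**Working it through.** **Step 1: put dose histories through the rules.** Inputs are the section 3.8 rules as quoted. *Only one dose* in (a) is taken to mean one dose in total, and the 14 days in the full rule are taken to apply to controls as well. Figures are days from each dose to the reference date: onset for cases, selection for controls. The last column reverses the control window in (b) and gives the unvaccinated line a matching control clause.

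| Doses | Case | Control, as written | Control, corrected |
|---|---|---|---|
| none | unvaccinated | unvaccinated | unvaccinated |
| one, at 10 | unvaccinated | **no category** | unvaccinated |
| one, at 30 | partial (a) | partial (a) | partial (a) |
| two, at 40 and 20 | full | **full and partial (b)** | full |
| two, at 36 and 15 | full | **full and partial (b)** | full |
| two, at 30 and 14 | partial (b) | **no category** | partial (b) |
| two, at 30 and 10 | partial (b) | **no category** | partial (b) |

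Each case history lands in exactly one category. Controls show one overlap and two gaps. The correction removes all three and reproduces the case column.

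**Step 2: who is affected.** Control group 1 (test-negative ILI), required in every study by section 3.7, has a symptom onset date. If onset alone is used, these controls follow the case column. If the selection date is used, they follow the third column. Section 3.8 does not say which applies, and these patients meet both descriptions. Controls without ILI have no onset, so only the selection date is available for them.

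**Step 3: size of the overlap effect on two-dose VE.** The protocol states no figure to reproduce here. Let f be the share of fully vaccinated controls filed as partial, with cases filed correctly. The fully vaccinated control count is multiplied by (1 − f), so

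observed OR = true OR / (1 − f), and VE = 1 − observed OR.

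The true OR is assumed to be 0.4, the detectable value in Table 2 (VE 60%). The values of f are also assumed.

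- f = 5%: 0.4/0.95 = 0.421, VE 57.9%
- f = 10%: 0.4/0.90 = 0.444, VE 55.6%
- f = 25%: 0.4/0.75 = 0.533, VE 46.7%

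**Step 4: direction of the other effects.** The same misfiled controls enlarge the partial control group, which lowers the one-dose OR and overstates one-dose VE. Dropping controls with a recent second dose shrinks that group and understates it. Dropping controls whose only dose is recent shrinks the unvaccinated reference among controls, which lowers the ORs and overstates VE. The net effect depends on how each team resolves the text.

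**The case against.** The intended meaning can be recovered. The full category comes first and uses the longer window for controls, the symptom half of (b) is its exact complement, and the seasonal rule in the same section treats cases and controls alike. The control parenthesis in (b) looks like a repeat of the one in (a), and many analysts would notice. This stands, but it does not make the text usable as written. No other section corrects it, and the revision clause covers dose number and immunisation delay, not this inconsistency.

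A reader might infer that the gaps affect all controls. The documents do not support that. Test-negative controls have an onset date and Annex 5 counts from onset, so the symptom clauses can classify them. Section 3.7 raises additional control groups under the seasonal vaccine, although it does not bar them for the pandemic vaccine and section 3.1 foresees various control sets. The gap for a recent second dose also rests on the two readings stated in step 1. If (a) meant that only one of the doses was old enough, such controls would be partial, but (b) would then be redundant for cases. If the full rule set no delay for controls, they would count as full, still unlike cases. The overlap survives either reading.

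A reader might also infer very large errors, such as a one-dose VE near 80%, or of −40%, when the truth is 30%. Those results need assumed prevalences and extreme handling. The first moves every fully vaccinated control into partial, which leaves none in the full category and makes two-dose VE impossible to estimate, so it would be seen at once. The second depends wholly on the gap for recent second doses.

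Finally, scope is limited. Dose-specific VE is a secondary objective, and panvacc, the one derived pandemic exposure the protocol specifies, does not use clause (b). Nothing here shows that the seasonal VE or the binary pandemic VE is wrong.

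**Conclusion.** The exposure rule is wrong as written. The overlap for controls with two doses more than 14 days before selection follows directly from the text. The two gaps are certain for controls without ILI, and possible for test-negative controls if they are classified by selection date. The consequence is possible differential misclassification in the pandemic one-dose and two-dose VE.

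Its size cannot be fixed from the documents, because it depends on how analysts resolve the overlap. Under the assumed true two-dose OR of 0.4, the loss is 2.1 percentage points if 5% of fully vaccinated controls are misfiled (60 − 57.9), 4.4 points at 10% (60 − 55.6) and 13.3 points at 25% (60 − 46.7). These are illustrations, not predictions. The windows must be reconciled before any dose-specific analysis.

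**What to change.** Rewrite the pandemic part of section 3.8 around one index date: symptom onset for cases and for test-negative ILI controls, and selection date for controls without ILI. Apply the same mutually exclusive windows to everyone:

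- **Full:** second dose more than 14 days before the index date.
- **Partial:** first dose more than 14 days before the index date, and either no second dose or a second dose less than 15 days before it.
- **Unvaccinated:** no dose, or first dose less than 15 days before the index date.

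The condition on the first dose in the partial line matters. Without it, someone with both doses inside 15 days would meet both the partial and the unvaccinated rule. Align panvacc and panvaccdelay in Annex 5 with this three-level variable. The change concerns classification for analysis only, not the vaccination schedule.

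The cost is a wording change and one recode. Annex 1 already collects both pandemic dose dates, the number of doses and the onset date. It lists no selection date, so a study that uses controls without ILI should confirm that it records one; section 3.8 needs that date in any case.

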# 1 Background

Influenza viruses constantly evolve, vaccines are reformulated every year. Therefore, vaccine effectiveness (VE) estimates from previous years cannot simply be carried over to subsequent years.

Conducting annual influenza VE estimates at the European level right at the beginning of a seasonal influenza epidemic/pandemic and monitoring VE along the course of the epidemic/pandemic is crucial in order to:

- decide on recommendations for the use of the vaccine;
- target complementary or alternative public health measures (e.g. antivirals) for segments of the population where the vaccine is less effective;
- allow more precise estimates of the impact of current vaccination strategies on the burden of disease to support vaccination campaigns;
- trigger further investigations on seasonal and pandemic vaccines (improve composition, use of adjuvants, need for booster doses);
- better manage and respond to expected reports of vaccine failures (especially during a pandemic); and
- counterbalance the reports of adverse events following immunisation by providing elements for adequate risk management and cost-effectiveness analysis.

The recent occurrence of the A(H1N1)v pandemic augments the importance of obtaining reliable and early vaccine effectiveness estimates for the pandemic vaccine. It takes approximately four to six months for the first supplies of strain-specific vaccines to become available once a new strain of influenza virus is identified and isolated. Consequently, by the time the vaccines are first administered, the virus already circulates and VE results are needed rapidly. In addition, vaccine availability is likely to increase over time – depending on vaccine production output and the licensing of additional vaccines, which means that IVE measurements need to be repeated over time during the pandemic. VE studies may help determining if the seasonal influenza vaccination is effective or interacts with pandemic vaccine in protecting against the A(H1N1)v virus.

Currently, only observational studies can be used to provide real-time estimates of influenza VE in Europe.

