#### **Collected information**

Collected information will include (see also Annex 1: List of variables, definition and coding):

- study identification: country and GP;
- case/control demographics;
- signs, symptoms;
- date of onset of ILI;
- date of swabbing;

- laboratory results;
- selected underlying chronic conditions (including diabetes, heart disease, chronic obstructing pulmonary disorder, renal diseases, and immunodeficiencies);
- number of hospitalisations for chronic diseases in the previous 12 months;
- total number of GP visits in the previous 12 months;
- smoking history;
- current season influenza vaccination including date;
- pandemic vaccination including number of doses, date, brand;
- influenza vaccination in the previous two seasons;
- pregnancy status;
- functional status;
- antiviral administration; and
- information on laboratory confirmed A(H1N1)v influenza since the beginning of the pandemic.

Pandemic vaccine: Collected data will be revised as more information on the vaccine and the target groups becomes available.

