#### Measure of effect

Vaccine effectiveness will be computed as VE = 1 - OR. An exact 95 % confidence interval will be computed around the point estimate. (For studies using the screening method, refer to the ECDC generic screening protocol.)

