# Annex 5: Generated/recoded variables

#### Table: Generated/recoded variables

Variable name	Туре	Values and coding	Definition
caseflu	Numeric (binary)	0 = No 1 = Yes	Indicates ILI case that is lab- confirmed for influenza.
ili	Numeric (binary)	0 = No 1 = Yes	Variable that corresponds to EU ILI case definition (coded using the symptoms in dataset).
panvaccdelay	Numeric (continuous)	Integer	Number of days between pandemic influenza vaccination date and onset date of symptoms (needs to be modified if 2 doses are required).
panvacc	Numeric (binary)	0 = No 1 = Yes	Coded as yes if >14 days between pandemic vaccination and onset of symptoms (needs to be modified if 2 doses are required).
seasvaccdelay	Numeric (continuous)	Integer	Number of days between seasonal influenza vaccination date and onset date of symptoms.
seasvacc	Numeric (binary)	0 = No 1 = Yes	Coded as yes if >14 days between seasonal vaccination and onset of symptoms.
swabdelay	Numeric (continuous)	Unique integer	Number of days between onset date of symptoms and swab date.
swabless4	Numeric (binary)	0 = No 1 = Yes	1 indicates less than 4 days between symptom onset and swab date. 0 indicates more than 3 days.
anychron	Numeric (categorical)	0 = No 1 = Yes 8 = Don't know	0 indicates no chronic disease. 1 indicates at least 1 chronic disease. 8 indicates no chronic disease reported as 'yes' and at least one chronic disease reported as 'unknown'.
smokcurr	Numeric (binary)	0 = No 1 = Yes	Current smoker (1) vs. former smoker or never-smoker (0).
hosp	Numeric (binary)	0 = No 1 = Yes	Not hospitalised for chronic disease in past 12 months (0). Hospitalized for chronic disease in past 12 months (1).
previousflu	Numeric (binary)	0 = No 1 = Yes	Vaccinated with seasonal flu in any of the two years prior to current season.
weekepi	Continuous	Integer	Week of first case coded as 1, subsequent weeks incremental.

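### People whose first or only dose was 0–14 days before onset are coded as unvaccinated, so VE is underestimated during roll-out if any protection starts before day 15

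*Protocol*

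**What the plan says.** Section 3.8 (Definition of vaccination status) places a person in the pandemic-vaccine reference group if he or she "has not received any vaccine or if he/she has received one dose less than 15 days before developing symptoms". Annex 5 carries this into the analysis variables, which are binary. The pandemic variable panvacc is "Coded as yes if >14 days between pandemic vaccination and onset of symptoms", and the seasonal variable seasvacc is "Coded as yes if >14 days between seasonal vaccination and onset of symptoms". Every other record takes the value 0, so a dose on days 0–14 falls in with no dose at all. The example models in Annex 6 use seasvacc as the exposure.

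The effect measure is fixed in section 3.13: "Vaccine effectiveness will be computed as VE = 1 - OR". Section 3.8 allows its definition to be revised if early clinical data show that one dose is enough or that "the immunisation delay is different from the currently assumed 14 days". A revision of that kind moves the cut-off. It still leaves people inside the new window in the reference group.

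No section excludes these people, gives them a category or plans a sensitivity analysis on the window. The data to separate them will exist: section 3.12 lists "pandemic vaccination including number of doses, date, brand", and the seasonal vaccination date is collected too.

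**The concern.** Day 14 is a working cut-off, and the protocol treats it as uncertain. If protection builds up before then, the comparison is no longer immune vaccinees against people without vaccine. It is immune vaccinees against a mixture of never-vaccinated and partly protected people. Cases become rarer in the reference group than they should be, the odds ratio moves towards 1 and VE is understated.

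The setting makes the mixture likely. The background section says that "by the time the vaccines are first administered, the virus already circulates and VE results are needed rapidly", and one pandemic objective is "to provide early VE estimates". Section 3.13 plans interim analyses and stratification by periods of vaccine availability. The share of recent vaccinees changes across such periods, so part of an apparent change in VE could come from the coding.

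**Working it through.** **The plan's own figure.** Tables 1 and 2 give 89 cases and 89 controls for coverage 0.5, OR 0.4, alpha 0.05 (two-sided assumed) and power 0.80. With controls at 0.5, the vaccinated proportion in cases is 0.4×0.5/(0.5 + 0.4×0.5) = 0.2857. The two-proportion formula gives 81 per group without continuity correction and 90 with it, so the stated 89 is reproduced to within one. OR 0.4, that is VE 60%, is used below as the true value.

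**Bias formula.** Let r be the share of coded-unvaccinated controls who were vaccinated 0–14 days ago, and v the average protection in that window. Relative to never-vaccinated people, the risk in the reference group is (1 − r) + r(1 − v) = 1 − rv. Hence OR_obs = OR_true/(1 − rv) and VE_obs = 1 − 0.4/(1 − rv).

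The documents give neither r nor v. Both are assumptions, shown as ranges:

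| r | v = 0 | v = 0.2 | v = 0.3 | v = 0.6 |
|---|---|---|---|---|
| 0.10 | 60.0% | 59.2% | 58.8% | 57.4% |
| 0.20 | 60.0% | 58.3% | 57.4% | 54.5% |
| 0.30 | 60.0% | 57.4% | 56.0% | 51.2% |

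For example, r = 0.2 and v = 0.3 give 0.4/0.94 = 0.426, so VE is 57.4%. The column v = 0.3 is what a linear rise from 0 to 60% over the window would average.

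**Is r of 0.1–0.3 plausible?** Assume linear uptake of c per week. At week t the window holds 2c and the immune group c(t − 2), so r = 2c/[1 − c(t − 2)].
- Week 4: c = 0.05 gives 0.10/0.90 = 0.11; c = 0.08 gives 0.16/0.84 = 0.19.
- Week 8: c = 0.05 gives 0.10/0.70 = 0.14; c = 0.08 gives 0.16/0.52 = 0.31.

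**Drift over time.** Assume uptake of 1% per day. Then r = 0.14/0.93 = 0.151 on day 21 and 0.14/0.58 = 0.241 on day 56. At v = 0.3 the observed VE is 58.1% and then 56.9%. Once uptake has stopped for more than 14 days, r = 0 and VE returns to 60%.

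**Low coverage.** At 10% coverage with half of the vaccinees recent, r = 0.05/0.95 = 0.053. Observed VE is 59.4% at v = 0.3 and 58.7% at v = 0.6.

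**After separation.** With the window group removed from the contrast, expected VE is 60% for any v.

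**The case against.** The strongest reply is that the bias is conditional. Taken literally, the protocol's 14-day delay means v = 0, and then there is none. The documents give no figure for protection inside the window. This stands, and the conclusion is worded accordingly. The protocol does, however, call its own delay an assumption open to revision, so a result that does not depend on it is preferable.

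The size is also modest. Window protection of 60% would mean full protection from the day of the dose. At 30% the loss is 1.2 to 4.0 points. At the 90/90 minimum with 50% coverage, the SE of log OR is √(1/45 + 1/45 + 1/25.7 + 1/64.3) ≈ 0.31, so the 95% interval for VE of 60% is roughly 26–78%. This also stands as to size, although imprecision does not excuse a bias that can be avoided. The week term in the example model and the period strata may help to show a drift, but within any week the reference group is still mixed.

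A reader might infer three stronger points that the documents do not support:
- **Internal inconsistency**, because a recent second dose leads to partial status while a recent first dose leads to unvaccinated status. One rule yields both: a dose counts only once it is more than 14 days old.
- **Added confounding**, because recent vaccinees resemble other vaccinees. No direction or size can be shown. Such people in the reference group make the two groups more alike on those traits, and the plan adjusts for several of them.
- **Greatest harm in the earliest estimates.** Under steady uptake the share of recent vaccinees rises with time (11–19% at week 4, 14–31% at week 8), and at 10% coverage the loss is under 2 points. Early estimates are exposed because they fall within roll-out, but the ranking depends on an uptake curve that the documents do not give.

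**Conclusion.** The coding is stated explicitly, is built into the derived variables and has no safeguard. If there is any protection before day 15, it understates VE while vaccination is in progress; this mechanism does not inflate VE. For a true VE of 60%, the observed value is about 51–59% for r of 0.1–0.3 and v of 0.2–0.6, and about 56–59% at v = 0.3. All of these rest on assumed r and v. The bias is zero at v = 0, follows the share of recent vaccinees, can drift across roll-out periods and ends once uptake has stopped for more than 14 days.

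The same coding applies to the seasonal vaccine, but no size is shown for it: nothing in the documents shows that seasonal uptake is still rising during the seasonal study period. This is a cheap improvement and does not invalidate the design.

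**What to change.** In section 3.8 and Annex 5:
- Define unvaccinated as no dose before symptom onset or, for controls, before the index date. The present pandemic clause refers to symptoms only and gives no date for controls without symptoms.
- Give people whose first or only dose was 0–14 days before that date their own level in panvacc and seasvacc, or exclude them from the main contrast. Apply this to cases and controls alike.
- Keep the present coding as a sensitivity analysis.

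No new data are needed, since vaccination dates are already collected. The cost is that these records leave the main contrast, so the minimum of 90 cases and 90 controls in section 3.13 should be counted without them. As an illustration, assume 50% coverage with a quarter of vaccinees recent. Then 12.5% of controls drop out: 90 × 0.875 ≈ 79 remain, and 90/0.875 ≈ 103 must be enrolled to keep 90. This may slightly delay early outputs.
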